#### **3 INVESTIGATIONAL PLAN**

#### 3.1 General Schema of Study Design

This is an open label, non-randomized, inter-subject dose escalation safety and tolerability study (Phase 1/2) of unilateral subretinal administration of two vector doses (up to  $5x10^{10}$  vg per eye and up to  $1x10^{11}$  vg per eye) in up to 15 subjects with choroideremia, with at least 2

weeks between vector administrations to successive subjects for the first two subjects of a given dose group (study-wide) and at least 2 weeks between vector administrations per clinical site for the rest of the subjects in the given dose group. The first dose cohort will contain five subjects, barring any dose limiting toxicity, and dose escalation will be contingent upon DSMB review of the safety data through at least 30 days for all subjects in the prior cohort. The second dose cohort will contain up to ten subjects.

Potential subjects will be recruited from the clinics of investigative team members, from vision centers, and self-referrals via the web-based posting in clinicaltrials.gov. After description of the clinical trial to the subject, using the study consent and other approved recruitment materials as educational tools, if the subject remains interested in study participation, he will be invited to consent for the gene therapy study. The gene therapy Screening/Baseline evaluations are comprehensive, and will consist of the review of all relevant medical records and tests required to determine study eligibility, including obtaining CLIA-certified laboratory confirmation of CHM genotype (if not done previously). If the subject is found eligible for the study and interested in pursuing the intervention phase, the subject will be scheduled for vector administration conducted under general anesthesia. The surgical procedure for this proposed study is similar to that conducted in the Phase 1 and Phase 3 studies of AAV2-hRPE65v2 (FDA BLA #125610, LUXTURNATM) and is described in the Manual of Procedures.

As is always the case with subretinal injection, the operating surgeon has latitude in administration of the dose, based on the pathophysiology of the subject's retina. In choroideremia in particular, it is anticipated that some patients will have limited access for injection due to degenerative disease. For this reason, all doses are specified as "up to 300  $\mu$ L," recognizing that some subjects may receive a smaller total subretinal volume than 300  $\mu$ L, and as such, may not receive the total dose. This information will be captured should this occur.

Following unilateral vector administration under general anesthesia, the subjects will be followed up comprehensively for safety and efficacy endpoints for two years after injection, then up to an additional 3 years (total of up to 5 years) of long-term follow-up. Based on the pathophysiology of choroideremia, the investigative team does not anticipate the nearly immediate improvement of light sensitivity, to the extent that resulted for the RPE65 gene therapy studies (Maguire *et al.*, 2008; Maguire *et al.*, 2009; Bennett *et al.*, 2012). Additionally, the visual deterioration of choroideremia generally progresses more slowly than that associated with autosomal-recessive *RPE65* gene mutations (Rosenberg & Schwartz, 1994; Roberts *et al.*, 2002). The slower decline of visual function of choroideremia means that the use of the uninjected eye as a control for the injected eye becomes more statistically significant as sufficient time lapses between injections. Therefore, to minimize risk to subjects, administration of investigational product will be done in one eye for this study.

#### 3.1.1 Screening/Baseline

Potential subjects will be referred from health professionals who care for patients with choroideremia, from clinics of investigative team members, from vision centers as well as potential self-referred subjects, and from the website posting on clinicaltrials.gov. For those patients who are interested, investigative team members will describe the clinical trial to the subject, using the IRB-approved study consent and other approved recruitment materials as educational tools. If the available clinical information indicates potential eligibility, and the

subject is interested in pursuing gene therapy, the subject will go through the consenting process, and sign informed consent for the gene therapy study, prior to initiation of Screening/Baseline evaluations. The gene therapy study Screening/Baseline evaluations are comprehensive, and will consist of the review of all relevant medical records and history, physical, ophthalmologic and laboratory evaluations required to determine study eligibility including obtaining CLIA-certified laboratory confirmation of CHM genotype (if not done previously). If all the inclusion criteria are met, and none of the exclusion criteria pertain (see section 3.4), the subject is eligible for the study. If the subject wishes to pursue the intervention phase, the subject will be scheduled for subretinal vector administration conducted under general anesthesia.

#### 3.1.2 Study Intervention

As stated in section 3.1.1 above, if after all the applicable Baseline evaluations, the subject is eligible for the study and wishes to pursue the study intervention phase, he will be scheduled for subretinal administration of the investigational product. Preoperative tests will be obtained as well as anesthesia consultation. If the pre-operative tests and the anesthesia consultation confirm acceptability for general anesthesia, the subject will be taken to surgery, placed under general anesthesia, and receive one of two different doses of vector, prepared by the investigational pharmacy. If baseline tests, preoperative tests, or anesthesia consultation should not indicate eligibility, vector administration will be postponed until a date at which eligibility criteria are met, or the subject will be withdrawn from the study. The vector will be administered unilaterally, to the subretinal space, under general anesthesia according to the procedure described in the Manual of Procedures. The eye with worse visual acuity will be injected.

Following vector administration, the subject will be kept in a supine position, observed and routinely monitored until stable. If no adverse events ensue, and the subject can maintain a supine position, the subject will be discharged during the 24-hour post-recovery period and scheduled for follow-up evaluation as an outpatient.

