Study Design	Open label, non-randomized, inter-subject dose escalation safety study (Phase $1/2$ ) of two vector doses (up to $5x10^{10}$ vg per eye (Dose Group 1) and up to $1x10^{11}$ vg per eye (Dose Group 2)) administered unilaterally, with at least 2 weeks between vector administrations to successive subjects for the first two subjects of a given dose group (study-wide) and at least 2 weeks between vector administrations per clinical site for the rest of the subjects in the given dose group. The eye with worse visual acuity will be injected, unless the subject prefers that eye, in which case the contralateral (non-preferred) eye will be injected. Five subjects will be entered to Dose Group 1 (subjects 1-5) and ten to Dose Group 2 (subjects 6- 15). Dose escalation will be contingent upon Data Safety Monitoring Board (DSMB) approval following review of safety data of the prior cohort through at least a minimum of 30 days (that is, at least 30 days after the last subject of the previous cohort is injected).

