potential eligibility, gene therapy informed consent is conducted prior to the extensive Baseline evaluation. The Baseline evaluation will be comprised of medical history and comprehensive visual and laboratory assessments (including confirmation of genetic diagnosis if adequate records are not available). If all of the criteria indicate study eligibility, the subject is offered the opportunity of vector administration and participation in the active phase of the study.
Study Intervention (Vector Administration) : After confirmation of eligibility and subject agrees to study entry, the investigational product (AAV2-hCHM) is administered in the operating room on Day 0 via unilateral subretinal injection under general anesthesia to the subject's non-preferred eye (or the eye with worse visual acuity if the subject has no preference). The subject is maintained for up to 24 hours in a supine position following the procedure. The subject may be discharged during this 24-hour time period, if stable, provided the post-operative supine positioning can be maintained.
Active Phase Follow-Up: Analyses will include safety endpoints such as adverse events, comprehensive blood and urine laboratory tests, vector presence in blood and tears, pregnancy outcomes (in female partners of subjects), as well as ophthalmologic safety and efficacy endpoints including ophthalmic examination, and measures of visual function, functional vision, ophthalmologic imaging, and quality of life (QOL) questionnaire. The schedule of evaluations in the active phase will be conducted over an approximately 2-year period post vector administration to assess safety and efficacy of AAV2-hCHM (including the administration), comparing the findings obtained longitudinally from the injected eye with those of the uninjected eye serving as the control.

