Visual Acuity	X		Х	Х	X1	Х	Х	Х	Х	Х	х	Х	х	Х
Visual Field Test, Humphrey	X						Х	Х	Х	Х	х	Х	Х	Х
Visual Field Test, Goldmann	X											Х		Х
Visual Field Test, Octopus 	X 						X4	X 	X4	X4	X 	X4	X 	X4
Reading Speed	X						Х	Х	Х	Х	х	Х	х	Х
Contrast Sensitivity	X						Х	Х	х	Х	х	Х	х	Х
Color Vision Test	X						Х	Х	х	х	х	х	х	Х
Microperimetry	X						Х	Х	Х	Х	х	Х	Х	Х
Full-Field Light Sensitivity Threshold Testing	X						Х	Х	Х	Х	х	Х	Х	X4
Fundus Photography (with low intensity autofluorescence)	X						Х	Х	Х	Х	х	Х	Х	Х
OCT	X						Х	Х	Х	Х	х	Х	Х	Х
Quality of Life Questionnaire	X						Х	Х	Х	Х	х	Х	х	Х
Administration of AAV2-hCHM 		X												
AE Recording	X	X	Х	X 	$\mathbf{X}^{1}$	X	Х	X	X	Х	X	X	X	X
Partner Pregnancy Outcome Recording										х	х	X	X	X
Concomitant Medication Recording	X	X	X	X1	X1	X	X	X	X	X	X	X	X	X

Notes for Table of Clinical Assessments:

 Day 7 evaluations, including an additional ophthalmic exam, will only be conducted if ocular inflammation is present at the Day 3 visit  Blood/tear polymerase chain reaction (PCR) will be continued until two consecutive specimens test negative: Tear and blood collection will occur at each study visit until this result is obtained

 Day 0 = Day of vector administration: Unilateral subretinal dosing of AAV2-hCHM is conducted in the subject's non-preferred eye (or the eye with worse visual acuity if the subject does not have a preference) starting sequentially first with the Dose Group 1 (subjects #1-5, up to  $5x10^{10}$  vg/eye) followed by Dose Group 2 (subjects #6-15, up to  $1x10^{11}$  vg/eye). It should be noted that the degenerative component of the disease may preclude delivery of the full dose, in which case the dose given will be based on vector concentration and total volume administered (up to 300  $\mu$ L).

 Octopus kinetic visual field test will only be done to subjects whose central visual field is  $>20^{\circ}$  in at least 1 of the 24 meridians at the Screening/Baseline visit using Goldmann perimetry III4e isopter.

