#### 3.4 Study Population (Eligibility Criteria)

#### 3.4.1 Inclusion Criteria

- 1. Willingness to adhere to the clinical protocol and 5-year long-term follow-up as evidenced by written informed consent
- 2. Male at least 18 years of age
- 3. *CHM* gene mutation (confirmed by a CLIA-certified laboratory)
- 4. Central visual field (VF) < 30° in at least 6 of the 24 meridians (using Goldmann perimetry III4e isopter) in the eye to be injected for the initial three subjects in Dose Group 1; central visual field (VF) < 30° in any of the 24 meridians (using Goldmann perimetry III4e isopter) in the eye to be injected for the remainder of subjects. Central visual field is defined as field contiguous with fixation, not including isolated islands.
- 5. Any evidence of functioning outer retinal cells within the central 10°, as defined by intact visual field, optical coherence tomography (OCT) evidence of preserved outer

nuclear layer in the retina, or ophthalmologic evidence of intact retinal pigment epithelium, as detected by ophthalmoscopy and confirmed by fundus photography

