## 3.4.2. Exclusion Criteria

- 1. Females and individuals less than 18 years of age
- 2. Unwilling to use barrier contraception methods for a period of four months following vector administration
- 3. Previous history of ocular inflammatory disease (uveitis)
- 4. Prior intraocular surgery within six months
- 5. Participation in a previous gene therapy research trial within one year of enrollment or participation in any other ocular gene therapy trial
- 6. Participation in a clinical study with an investigational drug in the past six months
- 7. Grossly asymmetrical disease, or other eye morbidity, which may render the contralateral eye ineffective as a control. Grossly asymmetric disease would include situations where one eye has significantly worse visual acuity (defined as a difference of more than 15 letters on an ETDRS chart) or significantly worse visual field (defined as a difference of  $> 10^\circ$ ) than the other eye

[Note: Intraretinal fluid and/or cystoid macular edema are not exclusion criteria due to the prevalence of these findings in patients with choroideremia.]

- 8. Visual acuity < 20/200 on standard ETDRS testing in the eye to be injected
- 9. Presence of disease which may preclude the subject from participation in this trial, for example, cornea or lens disorders that impede retinal evaluation, systemic disease causing retinal changes such as diabetic retinopathy, neurologic disease which may confound study endpoints, malignancies which may be treated by local therapies (e.g., radiation) to the eye or CNS, or hematologic or other diseases which may complicate assessment of research outcomes; primary or acquired immune deficiency, because of the increased risk of opportunistic infections, such as CMV retinitis
- 10. Use of medications known to be neuroprotective and possibly beneficial for retinal disease (such as valproic acid) or retino-toxic (such as isotretinoin, thioridazine, chloroquine, and hydroxychloroquine) that could potentially interfere with the disease process and/or cause ocular adverse events; individuals who discontinue use of these compounds for 6 months may become eligible
- 11. Individuals incapable of performing visual function testing, *e.g.* visual field and microperimtery, for reason other than poor vision

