#### 4.2 Study Intervention Phase

If results of the Screening/Baseline evaluations indicate eligibility, and the subject agrees to study entry, vector (the investigational product) administration will be scheduled. On the day of surgery, vital signs, chemistry, hematology, and urinalysis, will be performed, along with specimen collection for vector shedding (Section 4.2.1). If the anesthesia consult clears the subject for general anesthesia, the subject will proceed with vector administration under general anesthesia (Section 4.2.1). After vector administration (study intervention), there are regularly scheduled post-administration tests scheduled over a two-year interval to assess both safety and efficacy (Section 4.2.2), as well as for an additional up to 3 years, for a total of up to 5 years LTFU following vector administration (Section 4.5). Pregnancy outcomes will be collected after female partners of subjects consent and authorize collection of medical information. Subjects are encouraged to inform the Investigators as soon as a pregnancy occurs and when the outcome of the pregnancy is known.

The subject's non-preferred eye, or the eye with worse visual acuity if the subject has no preference, will be the one receiving the vector administration at the time of surgery. This would allow subjects to preserve the better eye in the event that the study product or procedures result in further visual deterioration. In patients with choroideremia, the visual function of each eye generally parallels that of the contralateral eye.

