## 3. INVESTIGATIONAL PLAN

### 3.1 Study Design

This is an open label, non-randomized, inter-subject dose escalation safety study (Phase 1/2) of two vector doses (up to  $5x10^{10}$  vg per eye (Dose Group 1) and up to  $1x10^{11}$  vg per eye (Dose Group 2)) administered unilaterally, with at least 2 weeks between vector administrations to successive subjects for the first two subjects of a given dose group (study-wide) and at least 2 weeks between vector administrations per clinical site for the rest of the subjects in the given dose group. The eye with worse visual acuity will be injected, unless the subject prefers that eye, in which case the contralateral (non-preferred) eye will be injected.

Five subjects will be entered to Dose Group 1 and ten to Dose Group 2. All subjects must meet entry criteria detailed in the Protocol Section 3.4. Dose escalation will be contingent upon DSMB review of the safety data through at least 30 days for all subjects in the prior cohort. Subjects will be followed up for safety and efficacy evaluations for approximately 2 years post vector administration, then additional 3 years of long-term follow-up. See Appendix A for the Schedule of Assessments.

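### Protocol 3.1.2 drops the preference rule for choosing the study eye, so for a subject who prefers his worse-acuity eye it names the wrong eye for injection

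*Protocol*

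**What the plan says.** Protocol 3.1.2 (Study Intervention) closes its description of vector administration with the sentence "The eye with worse visual acuity will be injected". It gives no exception and does not refer the reader to another section for the choice of eye.

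Six other places give a rule that depends on preference:

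- Protocol Synopsis, Study Design: the worse-acuity eye, "unless the subject prefers that eye, in which case the contralateral (non-preferred) eye will be injected".
- Protocol Synopsis, Study Intervention (Vector Administration): the non-preferred eye, with acuity deciding if there is no preference.
- Protocol Table of Clinical Assessments, note 3: the same rule.
- Protocol 4.2: the non-preferred eye, "or the eye with worse visual acuity if the subject has no preference, will be the one receiving the vector administration".
- SAP 3.1: "The eye with worse visual acuity will be injected, unless the subject prefers that eye", in which case the other eye is used.
- SAP Appendix A, note 3: the same rule as the Protocol's note 3.

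Two eligibility criteria are tied to the eye that will be treated. Inclusion 4 sets its visual field limit "in the eye to be injected for the initial three subjects in Dose Group 1", with a looser limit on the treated eye for later subjects. Exclusion 8 reads "Visual acuity < 20/200 on standard ETDRS testing in the eye to be injected".

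**The concern.** Section 3.1.2 is a complete, mandatory sentence in the Investigational Plan, under the heading where a reader would look for this rule. The Synopsis and SAP 3.1 expressly foresee a subject who prefers his worse-acuity eye. The missing clause is therefore the one written for him.

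Three things are at stake for such a subject:

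- **Safety.** Protocol 4.4 and SAP 3.2.4 say the treatment cannot practically be withdrawn. Protocol 9.4.2 lists macular hole and reduced acuity among the procedure risks and gives complete loss of vision as the worst outcome. Following 3.1.2 would put that risk on the eye he wants kept.
- **Eligibility.** Inclusion 4 and exclusion 8 would be applied to a different eye, so whether he can enter may depend on the section followed.
- **The record.** Enrolment violations must be reported (end of Protocol 3.4) and all deviations are listed (SAP 5.2). Whichever eye is injected, one section is followed and another is breached.

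**Working it through.** No sample size, power or error-rate figure is involved, so the check is a comparison of the texts followed by one eligibility illustration.

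**Count.** Statements with the preference rule: 4 in the Protocol + 2 in the SAP = 6. Statements without it: 1 (Protocol 3.1.2).

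**Eye named in each case, where the two eyes differ in acuity:**

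| Subject's preference | Protocol 3.1.2 | The six other statements |
|---|---|---|
| None | Worse-acuity eye | Worse-acuity eye |
| Better-acuity eye | Worse-acuity eye | Worse-acuity eye (non-preferred) |
| Worse-acuity eye | Worse-acuity eye (preferred) | Better-acuity eye (non-preferred) |

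The two forms of the preference rule, one worded as an exception and one as the main rule, name the same eye in every row. Only the last row conflicts, and there the eyes are opposite.

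**Can eligibility turn on this?** Exclusion 7 removes subjects whose eyes differ by more than 15 ETDRS letters; exclusion 8 removes those whose treated eye is below 20/200. Assume 0.02 logMAR per letter, a figure the documents do not give.

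- 20/200 in logMAR: log10(200/20) = 1.00.
- Largest difference allowed by exclusion 7: 15 × 0.02 = 0.30.
- Preferred eye one letter below 20/200: 1.00 + 0.02 = 1.02.
- Best fellow eye still allowed by exclusion 7: 1.02 − 0.30 = 0.72, or 20/(20 × 10^0.72), about 20/105.
- Worst fellow eye still allowed by exclusion 8: 1.00, or 20/200.

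A fellow eye at exactly 20/100 (logMAR 0.70) is just out of range: (1.02 − 0.70)/0.02 = 16 letters, so exclusion 7 would remove the subject under either rule.

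More generally, if the preferred eye is k letters below 20/200, the fellow eye must lie between 0.70 + 0.02k and 1.00. That range exists for k = 1 to 15, since 0.70 + 0.02 × 15 = 1.00.

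For any such subject the acuity part of exclusion 7 does not apply under either rule. Under 3.1.2 the treated eye is the preferred one, below 20/200, and exclusion 8 removes him. Under 4.2 the treated eye is the fellow eye, at 20/200 or better, and exclusion 8 does not.

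**Effect on comparisons.** Exchanging the eyes reverses the sign of every non-zero baseline difference between treated and control eye. Acuity is the one measure known to differ in this subject.

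**The case against.** The best reply is that nobody would be misled. Section 3.1.2 is an overview under the General Schema. The dedicated procedures section, 4.2, states the full rule and its reason, which is to spare the better eye if treatment does harm. The note attached to Day 0 dosing and both Synopsis statements agree with 4.2. A site would have to follow one sentence against four Protocol statements and the subject's own wish. Section 3.1.2 also refers to the Manual of Procedures for the administration procedure; that manual is not available here and may settle the matter.

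Much of this stands. It makes an actual error unlikely and keeps the point minor. It does not make the sentence right: the Synopsis and the schedule note are summaries too, and they keep the preference rule.

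The eligibility example is also narrow. It needs a subject who prefers an eye below 20/200 to a better-seeing fellow eye that is itself near the limit. For inclusion 4, an effect is possible but no case is worked here. Exclusion 7 limits field asymmetry to 10°, and Protocol 4.2 says the two eyes generally run in parallel, so any divergence is bounded.

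On analysis the objection is right. SAP 6 and 6.1 treat efficacy as exploratory and list results by injected and control eye, so the listings follow whichever eye was treated.

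**Conclusion.** The concern holds and is minor. It is an internal inconsistency in an operative rule: 3.1.2 is wrong as written, and the intended rule is plain from six other statements. It affects only a subject who prefers his worse-acuity eye, and the documents do not show that any such subject was enrolled. For him the injected eye is reversed and the control eye with it, and his eligibility may change. The eligibility illustration rests on the assumed 0.02 logMAR per letter; the conflict over the eye does not. No planned number or analysis changes.

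**What to change.** Replace the sentence in Protocol 3.1.2 with the rule in Protocol 4.2, word for word: the non-preferred eye is injected, and acuity decides only when the subject has no preference. This also settles which eye inclusion 4 and exclusion 8 refer to.

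The cost is one protocol sentence. Because the choice of eye bears on subject safety, Protocol 9.4.1 calls for IRB and DSMB approval and submission to the IND; the change can go in with the next amendment. The SAP, data collection and listings need no change.
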